## **7.2 Adverse Event Management Protocol**

Mild adverse events (Table 2, Category A) encountered by any subject regardless of assigned treatment will be recorded, relayed to the safety monitoring team and closely followed by the TN. More concerning adverse events (Category B) will be managed by withholding the study intervention for 2-4 weeks pending resolution of symptoms or biochemical abnormalities. Subjects will then be restarted on the lower dose (40 mg/day) of the study intervention (atorvastatin or placebo). Depending on the dose at which adverse events occurred, the process can be repeated, tapering the dose down to attrition as deemed appropriate by the PI in consultation with the external medical safety monitor (MSM). Intolerable or potentially serious adverse events that recur or persist in spite of dose reduction, along with other serious adverse events listed in Section 8 will lead to unblinding and determination of endpoint for that subject in the trial. A statin expert physician consultant is available at the Chicago site to advise regarding adverse event management in individual cases.

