### **7.3.3 Hepatotoxicity**

Drug-induced liver insult runs a spectrum from asymptomatic elevation of liver enzymes to acute fulminant hepatitis. However, it is now well recognized that statin-related hepatic adverse events are exceptionally rare and unpredictable. Analysis of safety data pooled from 49 clinical trials of atorvastatin in 14,236 patients showed that persistent elevation in hepatic transaminases does not exceed 0.6% (106). Statin-induced liver insult almost invariably occurs in cases with pre-existing chronic liver disease (e.g. viral/ alcoholic hepatitis, etc.) or concomitant ingestion of hepatotoxic drugs (25, 102, 103). All subjects in this study will be screened for risk of hepatic toxicity prior to enrollment, as per current recommendations by both the American College of Cardiology/American Heart Association (ACC/AHA) and FDA (107). The FDA has recently revised safety guidelines to remove the need for routine monitoring of liver enzymes in patients taking statins. To detect asymptomatic elevation of liver enzymes, enrolled subjects will also have their liver enzymes checked at 3 months and at each follow up visit. Additionally, subjects exhibiting any evidence of liver dysfunction at any point throughout the trial will undergo extensive hepatitis workup and further management in accordance with the trial adverse events management algorithms. (Table 2)

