• Hepatitis (0.6%)	Elevated Transaminases (ALT, AST): <ULN - 3.0 x ULN, no relevant clinical symptoms.	Elevated Transaminases (ALT, AST): >ULN - 3.0 x ULN, no relevant clinical symptoms.	Recurrence after dose reduction / ALT >3.0 ULN; >3 x ULN with the appearance or worsening of fatigue, nausea, vomiting, right upper quadrant pain or tenderness, fever, rash, or eosinophilia
• Acute Liver failure			Hepatitis plus abnormal plasma levels of ammonia, bilirubin, lactic dehydrogenase, and alkaline phosphatase
• Cholestasis		Serum conjugated bilirubin >1.5 x ULN; clinical jaundice.	Recurrence after dose reduction
• Pancreatitis			Severe abdominal pain; vomiting plus enzyme elevation (amylase 200 above ULN with elevated lipase levels) or radiologic findings
Nervous System			
• Dizziness, insomnia (3%), Depression, nightmares	Tolerable, self-limited	Intolerable/persistent	Recurrence after dose reduction

Adverse Event Category	Mild AE (Category A)	Moderate AE (Category B)	Serious AE (Category C)
• Cognitive impairment	1 points drop in MMSE; not interfering with work/school/life performance; specialized educational services/devices not indicated	>1 points drop in MMSE; interfering with work/school/life performance; specialized educational services/devices not indicated	Persistence after dose reduction
• Symptomatic Intracerebral Hemorrhage			New onset neurological symptoms Plus intraparenchymal or intralosomal hemorrhage confirmed on imaging studies
Endocrine system			
• Hyperglycemia		New impaired glucose tolerance/glycemic control	Persistence after dose reduction
Respiratory			
• Nasopharyngitis (8.3%)	Tolerable, self-limited	Intolerable/recurrent	Recurrence after dose reduction
• Epistaxis	Mild episode, self-limited	Requiring medical attention, Recurrent episodes	Recurrence after dose reduction
Genitourinary			
• Urinary tract infection (5.7%)	Simple cystitis	Recurrent cystitis /pyelonephritis	Recurrence after dose reduction

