## 8. CRITERIA FOR INTERVENTION DISCONTINUATION

Atorvastatin/Placebo administration will be discontinued for any of the following reasons (designated as serious AEs or Category C in the preceding Table 2):

- Symptomatic intracerebral hemorrhage (ICH) whether primary, arising from index cavernous malformation that previously bled, or in other lesion, or other ICH of any kind
- Severe allergic reaction
- Rhabdomyolysis
- Markedly elevated liver enzymes
- Liver failure
- Pancreatitis
- Pregnancy
- Intolerable adverse events that persist or recur after serial dose reduction.
- In the investigator's judgment, withdrawal from the trial would be in the subject's best interest (Drug interaction/glycemic control).
- The subject or legal representative withdraws consent, or patient undergoes surgical resection or irradiation of CCM lesion, other brain surgery or irradiation for any cause.
- Patient develops clinical indications for statin use for cholesterol or cardiovascular indications unrelated to CCM.

If one or more of these events occur after commencing the study drug, the subject will be considered to have reached a safety endpoint. Study drug or placebo shall be discontinued. All subjects reaching safety endpoints will be followed through the 24-month follow up visit as a part of the outcome assessment for the study. An attempt will be made to contact subjects who withdraw from the study or who are lost to follow up for safety evaluation. If these subjects wish not to cooperate there will be no additional follow up.

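### Table 2, hepatitis row: a symptom-free ALT or AST above ULN and up to 3.0 × ULN meets both Category A and Category B, and the protocol does not say which action applies

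*Combined protocol and SAP*

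**What the plan says.** Table 2 grades statin-related adverse events as A (mild), B (moderate) or C (serious). Its hepatitis row reads:

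- Category A: "Elevated Transaminases (ALT, AST): <ULN - 3.0 x ULN, no relevant clinical symptoms"
- Category B: "Elevated Transaminases (ALT, AST): >ULN - 3.0 x ULN, no relevant clinical symptoms"
- Category C opens with "Recurrence after dose reduction / ALT >3.0 ULN". It then adds values above 3 × ULN accompanied by listed symptoms, without naming an enzyme.

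Section 7.2 turns the category into an action. For A: "Mild adverse events (Table 2, Category A) encountered by any subject regardless of assigned treatment will be recorded, relayed to the safety monitoring team", with follow-up by the trial nurse and no change of dose. For B: "More concerning adverse events (Category B) will be managed by withholding the study intervention for 2-4 weeks", followed by a restart at 40 mg/day or matching placebo. Sections 3.4 and 5.1 also make Category B the trigger for the lower dose.

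Section 7.3.3 says that subjects with any evidence of liver dysfunction "will undergo extensive hepatitis workup and further management in accordance with the trial adverse events management algorithms. (Table 2").

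**The concern.** The two cells have the same upper limit and the same symptom wording, so they do not separate mild from moderate. For one liver result, the protocol supports both staying at 80 mg and a hold followed by 40 mg. Section 7.3.3 schedules liver enzymes specifically to find symptom-free elevations, so this row governs the results that the testing is meant to detect. What is at stake is consistent dose handling and consistent safety grading in a few subjects. The primary comparison is not at stake.

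**Working it through.** **Overlap.** Let x be ALT or AST divided by ULN, in a subject without relevant symptoms.

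- Category A as printed: x from below 1 up to 3.0.
- Category B as printed: x above 1 and up to 3.0.
- In both: x above 1 and up to 3.0, which is all of B. The only part of A outside B is x at or below 1, which is not an elevation.

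Example: a symptom-free ALT of 2 × ULN is A (stay at 80 mg, follow) and also B (hold 2-4 weeks, restart at 40 mg).

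**Could a misprinted sign explain it?** If A's sign was meant to be the one printed in B, the cells are identical and the overlap remains. If A means only values below ULN, the overlap goes, but A then labels normal values as elevated and no mild grade is left. Other numeric rows do separate A from B: CK below versus above 3 × ULN (the latter with a new ALT rise), and an MMSE drop of 1 point versus more than 1.

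**What the hepatitis row assigns:**

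| Result | Category |
|---|---|
| No symptoms, ALT or AST above 1 and up to 3.0 × ULN | A and B |
| No symptoms, ALT above 3.0 × ULN | C |
| No symptoms, AST above 3.0 × ULN | none named in the row |
| Symptoms, up to 3.0 × ULN | none |
| Listed symptoms, above 3 × ULN | C |

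**Search for a tie-break.**

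- Section 7.3.3 adds a workup, then refers management back to Table 2.
- Section 7.2 offers a statin consultant for individual cases, but no threshold.
- Section 8 lists marked liver-enzyme elevation, which does not separate A from B.
- Section 9.1 gives 40 mg for mild side effects. Table 2 labels A mild and B moderate, so this conflicts with Section 7.2 and settles nothing.

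**Subjects (40 on atorvastatin).** The only documented rate is in Section 7.3.3: persistent elevation not above 0.6%, threshold not stated. 0.006 × 40 = 0.24. Assumed range: 0.02 × 40 = 0.8 to 0.10 × 40 = 4. For comparison, Section 9.3.2 allows for up to 20% not tolerating 80 mg: 0.20 × 40 = 8.

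**Dose per affected atorvastatin subject if B is applied rather than A.** Planned dose over 730 days: 730 × 80 = 58,400 mg. Full adherence and no return to 80 mg are assumed.

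| Found at | 14-day hold | 28-day hold |
|---|---|---|
| Day 91 | 91×80 + 625×40 = 32,280 mg (55.3%) | 91×80 + 611×40 = 31,720 mg (54.3%) |
| Day 182 | 182×80 + 534×40 = 35,920 mg (61.5%) | 182×80 + 520×40 = 35,360 mg (60.5%) |
| Day 365 | 365×80 + 351×40 = 43,240 mg (74.0%) | 365×80 + 337×40 = 42,680 mg (73.1%) |

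Days without drug: 14/730 = 1.9% to 28/730 = 3.8%. The times are the 3- and 12-month tests in Table 1 and the 6-month liver test in Section 6.3.6.

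**The case against.** The strongest reply is that the choice goes to named clinicians and that either answer is acceptable. There is one site and one PI. The trial nurse judges relatedness with the statin expert (Section 7), any liver dysfunction gets a workup (7.3.3), and it is reviewed as a medical event of interest (10.4.1.3). Dose reduction is planned for, subjects who stop or reduce drug stay in the intention-to-treat analysis, and Section 2.2 treats 40-80 mg/day as active. This stands as a reason to rate the point low. It does not supply a written threshold.

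A second reply is that the rule may exist elsewhere. The nurse's algorithms (7.1) and the operations manual and trial-adapted adverse-event dictionary (10.3.2) are not in the documents, and a digit or factor may have been lost from a cell. Neither can be excluded. The protocol text as it stands still has the overlap.

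Four stronger readings are tempting, and the documents do not support them:

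- **Automatic discontinuation or unblinding.** Table 2 puts recurrence after dose reduction in Category C, and Section 8 opens "Atorvastatin/Placebo administration will be discontinued for any of the following reasons (designated as serious AEs or Category C in the preceding Table 2"). A reader might infer that a low symptom-free recurrence ends treatment and breaks the blind. But Section 8's list speaks of marked elevation and intolerable events, and the unblinding sentence in 7.2 concerns "Intolerable or potentially serious adverse events that recur or persist in spite of dose reduction". Neither clearly reaches such a case.
- **Conflict with entry criterion 4.2.9.** Accepting a modest baseline value and acting on a new, possibly drug-related rise to the same level are different decisions.
- **SAE status.** Section 10.4.1.2 says SAEs generally correspond to B and C but defines them by outcome, so grading a low ALT as B does not make it an SAE.
- **AST outside the protocol.** A symptom-free AST above 3.0 × ULN has no cell in the row, but Section 8's entry refers to liver enzymes in general. The gap is in the table, and Section 8 does not define how high counts as marked.

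**Conclusion.** The point holds as a minor safety-rule correction. As printed, A and B overlap over the whole of B, the two categories carry different actions, and the protocol gives no rule for choosing. The likely reach is below one subject to about four of 40 on atorvastatin. That range rests on an assumed 2-10%, because the documented 0.6% describes persistent elevation and is not the same event as a single value in the overlap. For an affected subject, the choice of B means 2-4 weeks off drug and about 54-74% of planned cumulative dose, depending on when the value is found. That is de-escalation the protocol already allows. No effect on the primary contrast, power or sample size follows from it. The reading of the text is firm; what remains uncertain is whether trial documents not seen here already contain a cut-point.

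**What to change.** Amend the hepatitis row of Table 2:

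- Make A and B mutually exclusive with one cut-point confirmed by the trial's clinicians. For illustration only: A = above 1 and up to 2 × ULN, B = above 2 and up to 3.0 × ULN, both without symptoms.
- Write the symptom-free limb of Category C as ALT or AST above 3.0 × ULN, so that the table matches Section 8's general reference to liver enzymes.
- Give symptomatic elevations up to 3.0 × ULN a category, for example B.
- Check that the trial nurse's management algorithms use the same limits.

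The cost is a short amendment to three table cells, with IRB approval and discussion with NINDS staff and the external consultants, as Section 9.4.1 requires. Visits, tests, sample size and analysis do not change.

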## **4.2 Exclusion Criteria**

- 4.2.1** Pre-menopausal women who are breastfeeding, pregnant or likely to get pregnant during the study period.
- 4.2.2** Prior surgical treatment of the hemorrhagic CCM lesion.
- 4.2.3** Failure to pass MRI safety screening (claustrophobic, metal implant, etc.).
- 4.2.4** Known allergy or intolerance to gadolinium.
- 4.2.5** Severely impaired renal function (eGFR < 60ml/min), active renal disease or status post-kidney transplants.
- 4.2.6** Statin therapy, for any indication, for more than 7 continuous days or greater than 14 total days within 12 months preceding enrollment.
- 4.2.7** Indication to use statin medication for current approved indication, unrelated to CCM.
- 4.2.8** Known allergy or intolerance to statins.
- 4.2.9** Liver dysfunction or active liver disease (including chronic viral hepatitis) defined as baseline serum transaminases levels twice the upper range of normal.
- 4.2.10** Previous diagnosis of skeletal muscle disorders of any cause (myopathy), or baseline creatine kinase levels five times the upper range of normal.
- 4.2.11** Currently treated with or likely to need treatment with one or more of prohibited medications listed in section 5.3.
- 4.2.12** Active drug or alcohol use or dependence that, in the opinion of the site investigator, would interfere with adherence to study requirements.
- 4.2.13** Serious illness (requiring systemic treatment and/or hospitalization) until subject either completes therapy or is clinically stable on therapy, in the opinion of the site investigator, for at least 30 days prior to study entry.
- 4.2.14** Any other condition that the investigator believes would pose a significant hazard to the subject if the investigational therapy were initiated, including conditions resulting in or precipitating myopathy (e.g. HIV, uncontrolled hypothyroidism).

- 4.2.15** In the investigator's opinion, the patient is unstable, and would benefit from a specific intervention rather than treatment with atorvastatin.
- 4.2.16** Inability or unwillingness of subject or legal guardian/representative to give written informed consent.
- 4.2.17** No documentation of valid healthcare insurance.
- 4.2.18** No medical record confirmation of a primary care physician or other provider of ongoing medical care.
- 4.2.19** Previous cranial irradiation or radiosurgical treatment.
- 4.2.20** Use of ritonavir as an oral drug for COVID-19

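### The hepatitis row of Table 2 puts mild asymptomatic transaminase elevations in two categories and leaves two other presentations in none

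*Combined protocol and SAP*

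**What the plan says.** The hepatitis row of Table 2 (Section 7.3.4) has three cells:

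- Category A: "Elevated Transaminases (ALT, AST): <ULN - 3.0 x ULN, no relevant clinical symptoms".
- Category B: "Elevated Transaminases (ALT, AST): >ULN - 3.0 x ULN, no relevant clinical symptoms".
- Category C: "Recurrence after dose reduction / ALT >3.0 ULN; >3 x ULN with the appearance or worsening of fatigue, nausea, vomiting, right upper quadrant pain or tenderness", followed by further symptoms and signs (fever, rash, eosinophilia).

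Section 7.2 turns categories into actions. Category A events "will be recorded, relayed to the safety monitoring team and closely followed by the TN". Category B events lead to a hold of 2-4 weeks and a restart at the lower dose, and Sections 3.4 and 5.1 also make Category B the trigger for dose reduction. Section 8 lists reasons for stopping study drug, describes them as the serious or Category C events of Table 2, and names the liver reason only as "Markedly elevated liver enzymes".

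Section 7.3.3 says that "subjects exhibiting any evidence of liver dysfunction at any point throughout the trial will undergo extensive hepatitis workup", and refers further management to the algorithms in Table 2. Exclusion 4.2.9 covers liver dysfunction "defined as baseline serum transaminases levels twice the upper range of normal", so a subject with a value between 1 and 2 x ULN can be enrolled.

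**The concern.** The row works as an algorithm only if every presentation lands in one cell. As printed, one group of presentations lands in two cells with different actions, and two groups land in none.

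The trial nurse and coordinator are the first contact for subjects and work from management algorithms (Section 7.1), so the table should be usable without interpretation. Where it is not, two subjects with the same laboratory values could be handled differently: one followed on full dose, the other held and restarted lower. Where no cell applies, the decision to continue, hold or stop is left to judgment, although the protocol otherwise specifies it in advance. At stake are consistent handling of a known statin risk and consistent drug exposure.

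**Working it through.** No sample size, power or event count is involved, so the check is to apply the cells as printed. Let m be the larger of ALT and AST, in multiples of ULN.

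- A: m up to 3.0, no symptoms (the printed lower bound is below ULN).
- B: m above 1 and up to 3.0, no symptoms.
- C: recurrence after dose reduction; or ALT above 3 with or without symptoms; or a value above 3 (enzyme not named) with symptoms.

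For a first event, so that the recurrence limb does not apply:

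| ALT (x ULN) | AST (x ULN) | Symptoms | Categories met |
|---|---|---|---|
| 0.8 | 0.8 | no | A |
| 1.5 | 1.5 | no | A and B |
| 1.9 | 1.9 | no | A and B |
| 3.0 | 3.0 | no | A and B |
| 1.5 | 1.5 | yes | none |
| 2.9 | 2.9 | yes | none |
| 3.5 | 2.0 | no | C |
| 2.0 | 3.5 | no | none |
| 2.0 | 10 | no | none |
| 2.0 | 3.5 | yes | C |
| 3.5 | 3.5 | yes | C |

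**Overlap.** Every asymptomatic value above ULN and up to 3.0 x ULN meets A and B together. Category A also takes in normal values under a label that says elevated, which suggests that a sign is wrong in the source or was misread from the PDF. Reversing either sign alone would make the two cells identical, not separate, but other lost characters cannot be excluded. The page itself should be checked.

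**Gap 1, symptoms with values up to 3 x ULN.** A and B both require the absence of symptoms. Apart from recurrence, every limb of C starts above 3 x ULN. A first event of ALT 2.9 x ULN with right upper quadrant pain meets nothing. This does not depend on the doubtful sign.

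**Gap 2, isolated AST.** A and B name ALT and AST and stop at 3.0 x ULN. The symptom-free limb of C names ALT only. Asymptomatic AST of 3.5 or 10 x ULN with ALT at 2 x ULN therefore meets nothing, again whatever the sign.

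**Do other rows close the gaps?** Fatigue, pyrexia and nausea have their own rows, but these grade by tolerability and persistence and do not use the enzyme level. Right upper quadrant pain and eosinophilia have no row. The cholestasis row needs raised conjugated bilirubin or jaundice. No other row covers an isolated asymptomatic AST rise.

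**Baseline.** A subject enrolled at 1.9 x ULN meets the A and B wording with no change from entry, because the row refers only to ULN. By contrast, the incipient-myositis row asks for an ALT elevation that is new.

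**The case against.** The strongest reply is that the protocol does not manage liver events from this row alone. The opening of Section 7 gives every notified adverse event at least a telephone evaluation, with advice on continuing study drug. Section 6.3.7 adds an unscheduled visit for a possible drug-related event. Section 7.2 provides a statin expert physician, and Section 7.3.3 requires a hepatitis work-up. Section 8 lets the investigator stop drug on judgment. Section 10.4.1.3 makes liver dysfunction a medical event of interest, with the same review as an SAE.

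All of this stands, and it rules out several stronger readings:

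- A reader might infer that a mild asymptomatic case is held while a more worrying symptomatic one is not. The text does not settle this, because the mild case also meets Category A, which carries no hold.
- A reader might infer that symptomatic liver injury below 3 x ULN has no rule anywhere. The provisions above show otherwise; what is missing is a category.
- A reader might think that Section 8 has no link to Table 2. Its lead-in makes that link. The difficulty is that it leads back to a Category C cell with a gap for AST.
- A reader might infer that a subject would lose the starting dose for an unchanged entry value. Sections 10.4.1.1 and 10.4.3 count a pre-existing condition as an adverse event only if it worsens, and Section 7 limits managed events to those at least possibly related to the intervention. That largely answers the point. The row does not say so, however, and Section 7.3.3 is triggered by any evidence at any time.
- A reader might infer that the adverse event comparison in Section 9.5 is misclassified. That analysis uses counts per patient and MedDRA preferred terms by body system, not Categories A, B and C.

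What the reply does not do is assign a category to either gap or resolve the overlap. The work-up rule in 7.3.3 and the stopping rule in Section 8 both return to Table 2.

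**Conclusion.** The point holds as an internal inconsistency and incompleteness in one table row, and it is minor. The two gaps follow from the printed words alone. The A/B overlap rests on the printed signs being those of the source document.

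Its size cannot be given as a count. The documents state no frequency for symptomatic elevations up to 3 x ULN, for isolated AST rises, or for baseline values between 1 and 2 x ULN, so any number of affected subjects would be an assumption. The one related figure is in Section 7.3.3, where persistent transaminase elevation on atorvastatin does not exceed 0.6%. Applied to 40 subjects on active drug, that is 0.006 x 40 = 0.24 subjects. It does not bound transient elevations, but it gives no reason to expect many. The case for change rests on the categories driving hold, dose-reduction and stopping decisions, and on the low cost of correction.

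**What to change.** Reconcile the hepatitis row with Sections 7.2 and 7.3.3 and with the Section 8 liver bullet, so that each combination of analyte (ALT, AST), level and presence of symptoms falls in exactly one category.

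1. Check the inequality signs in the Category A and B cells against the source, and make the two cells mutually exclusive.
2. Assign a category to symptomatic values up to 3 x ULN and to asymptomatic AST above 3 x ULN, and name the analyte in every limb of Category C.
3. Have the Section 8 bullet refer to the reconciled cell by name.
4. State in the row that the pre-existing-condition rule of Section 10.4.3 applies to baseline elevations admitted under 4.2.9.

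The thresholds and resulting actions are for the sponsor's clinicians to set. The cost is a wording amendment to one table row and one bullet, with no new tests or visits.

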**7.3.4 Other adverse events.**

Other commonly reported adverse reactions (incidence  $\geq 2\%$  and greater than placebo) regardless of causality, reported in patients treated with atorvastatin in previous placebo-controlled trials, such as nasopharyngitis, diarrhea and urinary tract infection, will be individually reported and managed as elaborated in section 7.2.

**Table 2 below summarizes potential adverse events by body systems that have been reported with the study intervention and other statin medications.**

Adverse Event Category	Mild AE (Category A)	Moderate AE (Category B)	Serious AE (Category C)
General/Constitutional			
• Malaise / Fatigue	Tolerable/self-limited	Intolerable/persistent	Recurrence after dose reduction
• Pyrexia	38.0 - 39.0 degrees C (100.4 - 102.2 degrees F). self-limited	Intolerable/persistent	Recurrence after dose reduction
• Allergic reactions	Erythema multiform	Mild self-limited classic allergic responses such as pruritis, hives or urticaria, cutaneous vasodilation ("flushing"), development of edema (peripheral or airway), peripheral vasodilation (hypotension), bronchospasm, and/or tachycardia.	Recurrence after dose reduction/Anaphylactic reaction/Steven-Johnson syndrome / Toxic epidermal necrolysis
Muscular			
• Musculoskeletal pain (3.5%), muscle spasm (3.6%), arthralgia (6.9%)	Tolerable/self-limited	Intolerable/persistent	Recurrence after dose reduction
• Joint swelling	Asymptomatic; clinical or diagnostic observations only.	Intolerable/persistent	Recurrence after dose reduction
• Incipient Myositis	CK < 3 x ULN, no relevant clinical symptoms.	CK >3 x ULN Plus new elevation of ALT, irrespective of musculoskeletal symptoms.	Recurrence after dose reduction
• Definite Myositis (0.08%)		Myalgia Plus markedly elevated serum creatine kinase >10 x ULN	Recurrence after dose reduction
• Rhabdomyolysis			Myositis Plus evidence of new renal impairment +/- other organ system failure

Adverse Event Category	Mild AE (Category A)	Moderate AE (Category B)	Serious AE (Category C)
• Tendon Rupture			Tendon Rupture
GI/Hepatobiliary			
• Pharyngeal pain (2.3%) , dyspepsia (4.7%), nausea (4%), bloating, eructation, flatulence or diarrhea (6.8%)	Tolerable, self-limited	Intolerable/persistent	Recurrence after dose reduction

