### **Analysis of Treatment Compliance**

Treatment compliance is crucial to validate the study objectives. A compliance threshold of 90% will be implemented for proposed analyses per treatment rendered. Drug adherence will be rigorously monitored through an innovative electronic system that will provide continuously streamed real time data in addition to confirmatory manual pill count at each follow up call and scheduled visits. Assessment of compliance is an integral component at every scheduled or unscheduled evaluation and will be based on the **electronically acquired data as well as the missed doses log in the case report form (CRF)**. *A subject will be deemed noncompliant with the study intervention if he/she misses more than 21 consecutive doses at any point, or accumulate a log of 75 missed doses throughout the study.* Treatment compliance shall be compared in atorvastatin versus placebo cases as one of the secondary aims of the study.

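### Table 2, Hepatitis row: every symptom-free ALT or AST above ULN and up to 3 x ULN falls in both Category A and Category B, which carry different dosing instructions

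*Combined protocol and SAP*

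**What the plan says.** The Hepatitis row of Table 2 (Section 7.3.4) has three cells.

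- Category A, mild: "Elevated Transaminases (ALT, AST): <ULN - 3.0 x ULN, no relevant clinical symptoms".
- Category B, moderate: "Elevated Transaminases (ALT, AST): >ULN - 3.0 x ULN, no relevant clinical symptoms".
- Category C, serious, opens with "Recurrence after dose reduction / ALT >3.0 ULN" and goes on to values above 3 x ULN accompanied by symptoms.

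Section 7.2 ties an action to each category. For the first it says: "Mild adverse events (Table 2, Category A) encountered by any subject regardless of assigned treatment will be recorded"; these events are then passed to the safety team and followed, with no dose change. Category B events are "managed by withholding the study intervention for 2-4 weeks pending resolution of symptoms or biochemical abnormalities", after which the subject restarts at 40 mg/day of atorvastatin or matching placebo. Section 8 lists the Category C reasons for stopping study drug.

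Section 7.3.3 schedules liver enzymes at 3 months and at each follow-up visit so that symptom-free rises are found. It adds a hepatitis workup for any sign of liver dysfunction and refers back to Table 2 for management.

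**The concern.** A threshold table that drives dosing has to give one answer per laboratory value. Here a symptom-free ALT of, say, 1.5 or 2.5 x ULN satisfies both the mild and the moderate cell. The trial nurse can follow the subject on 80 mg, or stop the drug for up to four weeks and halve the dose, and cite the same row for either decision.

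The choice also has a sequel. Only a subject who has been dose-reduced can meet the recurrence term in Category C. Category C is the level at which Section 8 discontinues study drug, and Section 7.2 adds unblinding for potentially serious events that recur or persist despite the reduction. Which of two overlapping cells is applied to the first mild value can therefore decide whether that path opens at all.

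**Working it through.** The plan gives no figure to reproduce. The check is a comparison of intervals, in multiples of ULN and for subjects without symptoms.

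**Step 1. Overlap, under each reading of the sign in Category A.** The sign in that cell may be a typing or text-extraction slip, so all plausible readings are tried.

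| Reading of the Category A sign | Category A | Category B | Values in both |
|---|---|---|---|
| As printed (less than) | up to 3.0 | above 1.0 to 3.0 | above 1.0 to 3.0 |
| Greater than | above 1.0 to 3.0 | above 1.0 to 3.0 | above 1.0 to 3.0 |
| Greater than or equal | 1.0 to 3.0 | above 1.0 to 3.0 | above 1.0 to 3.0 |

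In every case the shared set is the whole of Category B. As printed, the only values that belong to A alone are those at or below ULN, which are not elevated. The symptom term is the same in both cells and cannot separate them. Category C starts above 3.0, so it does not separate them either.

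**Step 2. Instruction per value.**

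| Symptom-free ALT/AST | Category | Action under 7.2 |
|---|---|---|
| Above 1 to 3 x ULN | A | record, follow, stay on dose |
| Above 1 to 3 x ULN | B | hold 2-4 weeks, restart at 40 mg/day |

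**Step 3. Does another section supply the cut?**

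- 7.3.3 adds a workup and points back to Table 2.
- 7.2 makes a statin expert available for advice, but states no threshold.
- 6.3.4 has laboratory results reviewed for suitability to continue, again without a threshold.
- 3.4 and 5.1 tie the lower dose to Category B and so depend on the same row. 9.1 describes the 40 mg dose as being for mild side effects, which does not help to separate mild from moderate.

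**Step 4. Is a cut normal in this table?** Yes. The Incipient Myositis row separates A from B at a CK of 3 x ULN. Most symptom rows separate A from B by tolerable or self-limited against intolerable or persistent. The Hepatitis row has neither device.

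**Step 5. Cost of one hold.** Treatment lasts 24 months, about 104 weeks. A hold costs 2/104 = 1.9% to 4/104 = 3.8% of that subject's dosing time. Spread over an arm of 40, one such hold is 1.9%/40 = 0.05% to 3.8%/40 = 0.10% of arm exposure. The restart dose of 40 mg/day lies within the 40-80 mg/day range that Section 2.2 treats as active on ROCK.

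**The case against.** The strongest reply is that this is a slip in one cell, in a single-site trial with a statin expert on hand and an external medical safety monitor, so that judgement will fill the gap. That limits the damage: sites cannot diverge, and Category A is not neglect, since 7.3.3 still calls for a workup. But consultation is not a threshold. Two people applying the row correctly can reach opposite dosing decisions.

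Three stronger readings are tempting, and the documents do not carry them.

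- **A subject could be held for the value they entered with.** Exclusion 4.2.9 is "defined as baseline serum transaminases levels twice the upper range of normal", so values above ULN and below 2 x ULN are admitted. The Hepatitis row does not mention baseline, while the Incipient Myositis row asks for a "new elevation of ALT, irrespective of musculoskeletal symptoms". However, Section 10.4.1.1 confines adverse events to findings not seen before or conditions the investigator judges to have worsened, and Section 10.4.3 treats a preexisting condition as an event only if it worsens. These rules largely cover an unchanged baseline elevation, so it is not a separate fault. They do not remove the overlap: for a subject normal at screening, any value above ULN is new.
- **A hold could make the subject noncompliant.** The compliance paragraph in Section 9.5 applies to a subject who "misses more than 21 consecutive doses at any point, or accumulate a log of 75 missed doses throughout the study". A hold of 2-4 weeks is 14-28 daily doses, so it can pass 21. This consequence needs the Category B reading, a hold longer than 21 days, and a directed hold counted as missed doses, which is not the natural meaning. It would also apply to every Category B hold in Table 2, so it is not a consequence of this row.
- **The treatment comparison could be biased.** The same blinded rule applies in both arms, and Section 9.3.2 keeps subjects who stop drug, or who do not comply, in follow-up and in the primary analysis.

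**Conclusion.** The row is wrong as written, and the matter is minor. Categories A and B coincide for all symptom-free ALT or AST values above 1 and up to 3 x ULN under any reading of the sign, while Section 7.2 gives them incompatible dosing actions. What turns on it is whether an individual is held and dose-reduced, and whether the recurrence route to Category C becomes available. That route is possible rather than automatic, because Section 7.2 leaves repeated tapering to the investigator in consultation with the safety monitor.

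There is no arm bias, and the effect on the intention-to-treat analysis is small. How many subjects would fall in the band cannot be derived: the documents give neither the distribution of transaminases at screening nor their variation on treatment, so no count is offered. The conclusion rests only on the table text as available, and on the absence of a cut elsewhere in the protocol.

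**What to change.** Make the bands mutually exclusive with one stated cut. A workable default is Category A from above ULN to 2 x ULN, Category B from above 2 to 3 x ULN, and Category C above 3 x ULN as now. Nothing in the documents requires 2 x ULN. It is convenient because it matches the 4.2.9 entry limit, so no value allowed at entry could by itself be Category B. The clinicians may prefer another explicit separator, such as a rise confirmed as persistent on repeat testing; Section 5.3.1 already allows liver tests to be repeated when clinically indicated.

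The cost is a wording change in one row of Table 2, with no new patients and no change to the analysis. The downside of the 2 x ULN cut is that values of 1-2 x ULN are followed rather than held, so mild rises are acted on somewhat later. There may also be an occasional extra liver test.
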